## 5. GENERAL METHODOLOGY AND CONVENTIONS

### 5.1. Hypotheses and Decision Rules

#### 5.1.1. Statistical Hypotheses

This is a Phase 1/2 First-In-Human (FIH) study to assess the safety, tolerability and immunogenicity of GBS6 vaccine administered with or without AlPO4 or placebo. No formal statistical hypothesis testing will be performed. An estimation approach will be used to assess the safety and immunogenicity objectives.

#### 5.1.2. Statistical Decision Rules

Statistical decision rules will not be utilized in this study. All analyses are considered descriptive in nature.

### 5.2. General Methods

Descriptive summary statistics will be provided for all endpoints. Unless otherwise explicitly stated, descriptive statistics for continuous variables are: n, mean, median, standard deviation, minimum and maximum. Descriptive statistics for categorical variables are: the proportion (%), n (the numerator) and N (the denominator) used in the proportion calculation.

Unless otherwise explicitly stated, all safety and immunogenicity summaries will be presented for subjects from both sentinel and expanded cohorts combined, by dose/formulation level and vaccine group (hereafter referred to as vaccine group) as defined below:

1. GBS6 (5 µg)/AlPO4

2. GBS6 (5 µg)/no AlPO4
3. GBS6 (10 µg)/AlPO4
4. GBS6 (10 µg)/no AlPO4
5. GBS6 (20 µg)/AlPO4
6. GBS6 (20 µg)/no AlPO4
7. Placebo

### 5.2.1. Analyses for Binary Data

#### 5.2.1.1. Immunogenicity Data

For immunogenicity results, the 2-sided 95% confidence intervals (CIs) based on exact (Clopper and Pearson) method will be provided for each vaccine group and blood sampling timepoint by GBS6 serotype for the proportion of subjects achieving a defined value for IgG concentration as defined in [Section 3.6](#).

The exact CIs for a proportion will be computed using the F distribution. If  $r$  is the number of responses and  $n$  is the number of subjects, then it follows that  $p = r/n$  is the estimate of the proportion of responses. An exact 95% confidence interval can be computed by solving the following 2 equations. For the lower limit  $P_L$ , use

$$P_L = \frac{rF_L}{(rF_L + (n - r + 1))}$$

and for the upper limit  $P_U$ , use

$$P_U = \frac{(r + 1)F_U}{(n - r) + (r + 1)F_U}$$

where  $F_L$  is the quantile from the F distribution for  $\alpha=0.025$ , with numerator degrees of freedom equal to  $2r$  and denominator degrees of freedom equal to  $2(n-r+1)$ .  $F_U$  is the quantile from the F distribution for  $\alpha=0.975$ , with numerator degrees of freedom equal to  $2(r+1)$  and denominator degrees of freedom equal to  $2(n-r)$ . When  $r$  equals 0,  $F_L$  should be set equal to 1.0 so  $P_L$  equals 0. When  $r$  equals  $n$ ,  $F_U$  should be set equal to 1.0 so  $P_U$  equals 1.

The CI using the F distribution is described in Collett, (1991).

### 5.2.1.2. Safety Data

Similarly, the exact 2-sided 95% confidence intervals (CIs) using the Clopper and Pearson method will be provided by each vaccine group for all primary safety endpoints, proportions of subjects reporting local reactions, systemic events, AEs, SAEs, and MAEs.

For tier-2 AEs only, 95% CIs for the difference in proportions between each vaccine group and placebo based on the Chan and Zhang method will be provided.

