#### 2.1.2. Primary Endpoints

The endpoints for the primary objective are listed below, in chronological order according to time of collection in the study:

- The proportion of sentinel-cohort subjects with clinical laboratory abnormalities following investigational product administration at the 1-week follow-up visit.
- The proportion of subjects reporting prompted local reactions within 14 days following investigational product administration (redness, swelling, and pain at the injection site).
- The proportion of subjects reporting prompted systemic events within 14 days following investigational product administration (fever, nausea/vomiting, diarrhea, headache, fatigue, muscle pain, and joint pain).
- The proportion of subjects reporting adverse events (AEs) within 1 month following investigational product administration.
- The proportion of subjects reporting medically attended adverse events (MAEs) and serious adverse events (SAEs) within 6 months following investigational product administration.

initiated in parallel and each site is only allowed to enroll subjects into 1 cohort at a time. Enrollment will proceed this way in a staggered fashion throughout the study (see [Table 1](#) below for a graphic description of the enrollment/escalation plan).

Blood will be collected at screening and at the 1-week postvaccination follow-up visit in all subjects enrolled in each sentinel cohort for hematology and chemistry assessments. CCI

For all subjects, blood will also be collected on the day of investigational product administration prior to study vaccination and 1 week, 2 weeks, 1 month, 3 months, and 6 months after vaccination for immunogenicity assessment. Local reactions and systemic events will be collected for 14 days after vaccination. AEs will be assessed up to 1 month after vaccination. SAEs and MAEs will be assessed through 6 months after vaccination. In addition, AEs occurring up to 48 hours after the Visit 5 and Visit 6 blood draws that are related to study procedures will be collected.

CCI

CCI

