**3.3. Number of Subjects**

Approximately 363 subjects will be enrolled, 52 at each dose level/formulation and 51 in the placebo group. An allocation target will not be set by sex; however, the intention is for sites to enroll at least 50% women within each dose level group. If there is a predominance of one sex enrolled, the sponsor may give direction to sites about sex-based enrollment. Refer to [Table 2](#) for a detailed description of the number of subjects per group. Subjects who withdraw or are withdrawn from the study after randomization will not be replaced, regardless of the reason for withdrawal.

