## 2.2. Study Design

This is a Phase 1/2, randomized, placebo-controlled, observer-blinded trial to evaluate the safety, tolerability, and immunogenicity of 3 ascending dose levels of GBS6 formulated with or without AlPO4 administered in healthy adults aged 18 to 49 years.

Approximately 363 healthy adults aged 18 to 49 years of age will be randomized to receive a single dose of 1 of 3 dose levels of GBS6 formulated with or without AlPO4 or placebo (saline control). This study will utilize a sentinel-cohort design CCI

. Refer to Table 2 for a detailed description of the number of subjects per group. Safety data through 14 days for subjects enrolled in each sentinel cohort will be reviewed and if deemed acceptable, enrollment of the expanded cohort will proceed at that same dose level.

Blood will be collected at screening and at the 1-week after vaccination follow-up visit for hematology and chemistry assessments in all subjects enrolled in each sentinel cohort.

CCI

For all subjects, blood will also be collected immediately prior to study vaccination on Day 1, and 1 week, 2 weeks, 1 month, 3 months and 6 months after vaccination for immunogenicity assessment. Local reactions and systemic events will be collected for 14 days after vaccination. Adverse events (AEs) will be assessed up to 1 month after vaccination. Serious adverse events (SAEs) and medically attended adverse events (MAEs) will be assessed through 6 months after vaccination. In addition, AEs occurring up to 48 hours after the Visit 5 (3 months after vaccination) and Visit 6 (6 months after vaccination) blood draws that are related to study procedures will be collected.

An internal review committee (IRC) will review the 14-day safety data from each sentinel cohort prior to determining if expanded enrollment should begin at that dose level and whether enrollment in the sentinel cohort at the next highest dose should begin.

This study will utilize an external data monitoring committee (E-DMC) for regular review of accumulating safety data and for ad hoc review if a stopping rule is met, to provide a review of safety findings and the IRC recommendations.

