#### **3.6. Safety Endpoints**

##### **3.6.1. Adverse Events**

The time period for reporting AEs for all subjects is from the time the informed consent is signed to 1 month follow-up visit (Visit 4). For all subjects, only MAEs and SAEs will be collected at Visit 5 (3 month) and Visit 6 (6 month) follow-up visits. Additionally, AEs occurring up to 48 hours after Visit 5 (3 month) and Visit 6 (6 month) that are related to study procedure (e.g., blood draw) will be collected for all subjects.

All AEs are collected on the case report form (CRF) and will be categorized according to the current version (at time of reporting) of the Medical Dictionary of Regulatory Activities (MedDRA).

An immediate AE is defined as any AE that occurred within the first 30 minutes after IP (see Section 7.8.2 Immediate Adverse Events of the protocol).

A MAE is defined as a nonserious AE that results in an evaluation at a medical facility.

[Redacted text block]

AEs will be captured and reported in accordance with Pfizer reporting standards.

A 3-tier approach will be used to summarize AEs. Under this approach, AEs are classified into 1 of 3 tiers. Different analyses may be performed for different tiers.

- Tier-1 events: These are prespecified events of clinical importance and, if any, are maintained in a list in the product's Safety Review Plan. There are no pre-identified tier-1 events for this study.
- Tier-2 events: These are events that are not tier-1 but are "common." A MedDRA preferred term (PT) is defined as a tier-2 event if there are 4 or more subjects in at least one vaccine group.
- Tier-3 events: These are events that are neither tier-1 nor tier-2 events.

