## 6.7. Safety Summaries and Analyses

### 6.7.1. Adverse Events

It should be recognized that most studies are not designed to reliably demonstrate a causal relationship between the use of a pharmaceutical product and an AE or a group of AEs. Except for select events in unique situations, studies do not employ formal adjudication procedures for the purpose of event classification. CCI

Adverse events will be reported in accordance with the Pfizer reporting standards. For tier 2 and tier 3 events, the proportion of subjects with AEs in each vaccine group will be presented. In addition, for tier 2 AEs, 2-sided 95% CIs for the difference in observed proportions between each vaccine group and the placebo will be constructed. Tier 3 events will be summarized as part of the overall AE summary.

Listings of subjects reporting any AE and immediate AEs will be generated.

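### Does comparing each dose group with one placebo group of 51, pooled over three staggered dose cohorts, distort the tier-2 adverse event differences?

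*SAP*

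**What the plan says.** Protocol 3.3 plans "52 at each dose level/formulation and 51 in the placebo group". Table 2, in both documents, divides the placebo subjects into 17 at each of the three dose levels, beside 52 with and 52 without AlPO4. Protocol Table 1 shows the dose cohorts opening one after another, each with a sentinel part of 40 and an expanded part of 81.

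SAP 5.2 combines sentinel and expanded subjects and presents safety results "by dose/formulation level and vaccine group (hereafter referred to as vaccine group) as defined below". The list that follows has six GBS6 groups and one placebo group. A preferred term becomes a "tier-2 event if there are 4 or more subjects in at least one vaccine group" (SAP 3.6.1). For such terms only, SAP 5.2.1.2 provides "95% CIs for the difference in proportions between each vaccine group and placebo based on the Chan and Zhang" method, and SAP 6.7.1 states that "2-sided 95% CIs for the difference in observed proportions between each vaccine group and the placebo will be constructed". SAP 5.1.2 gives the status of all of this: "All analyses are considered descriptive in nature".

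On timing, SAP 2.2 has the internal review committee look at each sentinel cohort's 14-day data before "determining if expanded enrollment should begin at that dose level and whether enrollment in the sentinel cohort at the next highest dose should begin". The protocol's design text, which in the public copy runs on directly after Section 2.1.2, says that cohorts are "initiated in parallel and each site is only allowed to enroll subjects into 1 cohort at a time".

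**The concern.** Tables 1 and 2 imply that a subject is randomized within a dose cohort, to one of two formulations or placebo. The strictly randomized control for a dose group is therefore the 17 placebo subjects of its own cohort. The other 34 were enrolled under another dose, partly at other times and possibly at other sites. If a common complaint became more frequent as enrollment moved from the low to the high dose, the pooled comparison would show an excess at the high dose and a deficit at the low dose with no vaccine effect at all. In a first-in-human dose-ranging study that could pass for a dose-related safety pattern, and the visible SAP plans no table of placebo by dose cohort that would expose it. The threshold of 4 subjects makes this look sharper: 4/52 against 0/51 already gives an interval just above zero.

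**Working it through.** **1. The plan's own counts.** 3 × 17 = 51 placebo. 52 + 52 + 17 = 121 = 40 + 81 per dose level. 3 × 121 = 363. All agree with Protocol 3.3 and Table 2. From other cohorts: 51 − 17 = 34, and 34/51 = 66.7%.

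**2. Size of the possible bias.** Let r be the background rates in the three cohorts, with no vaccine effect. Expected pooled difference for cohort k = r_k − mean(r) = (2/3) × (r_k − mean of the other two). Flat rates give 0. Rates of 5/10/15% give −5, 0 and +5 points. The documents give no background rates, so every rate below is an assumption.

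Coverage of zero by the 95% Chan-Zhang interval was found by enumerating all outcomes, 52 against the sum of three Binomial(17, r_k), at 2.5% per tail with the p-value maximized over the nuisance rate:

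| Assumed rates, low/middle/high | Coverage, low/middle/high dose (%) |
|---|---|
| 10/10/10% | 95.6 / 95.6 / 95.6 |
| 2/3/4% | 97.2 / 97.1 / 95.8 |
| 5/6.5/8% | 94.7 / 95.7 / 95.0 |
| 5/7.5/10% | 93.1 / 95.8 / 93.9 |
| 5/10/15% | 85.9 / 95.7 / 89.2 |
| 5/15/5% | 91.3 / 83.5 / 91.3 |

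Up to a doubling of the rate (5/7.5/10%) the loss is under 2 points. A clear loss needs the rate of a single preferred term to triple between cohorts.

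**3. What a same-cohort comparison would give.** Ratio of standard errors = √[(1/52 + 1/17)/(1/52 + 1/51)] = 1.42. At a 10% rate the approximate half-width is 16.4 points with 17 controls and 11.6 with 51. Exact intervals: 4/52 against 0/51 gives 7.7 points (0.1 to 18.6); 4/52 against 0/17 gives 7.7 points (−12.6 to 19.0). Against 0/17 it takes 15/52 before the interval lies above zero. For a true rise from 5% to 15%, the chance that the interval lies above zero is 37% pooled and 0.3% same-cohort.

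**4. Could a 3 × 17 placebo table reveal drift?** An exact homogeneity test at the 5% level detects 5/10/15% about 5.6% of the time, 5/7.5/10% about 2.1%, and 5/15/5% about 8.5%. False alarms by eye are far more frequent. One event among the own 17 and none among the other 34 puts the own-cohort rate 1/17 − 1/51 = 5.9 − 2.0 = 3.9 points from the pooled rate. With no drift, a gap at least that large occurs 48% of the time at a flat 5% and 62% at a flat 10%.

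**5. A tempting example.** Take 4/52 at one dose and a single placebo event among 51. The pooled difference is 4/52 − 1/51 = +5.7 points. If the event falls in the same cohort, the own-cohort difference is 4/52 − 1/17 = +1.8, which looks like a false alarm exposed. Without drift that happens one time in three. Otherwise the own-cohort difference is 4/52 − 0/17 = +7.7, above the pooled value. The contrast shows where one event happened to land, not drift.

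**6. Calendar separation.** Assume placebo splits 40:81 within a cohort, 17 × 40/121 = 5.6 sentinel and 17 × 81/121 = 11.4 expanded (the true split is redacted). If each step of Table 1 closes before the next opens, the controls with no overlap in time are:
- low dose: 11.4 + 5.6 + 11.4 = 28.4
- middle dose: 5.6 + 11.4 = 17.0
- high dose: 5.6 + 11.4 + 5.6 = 22.6

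The visible text does not require that closure. If the low-dose expanded cohort is still enrolling when the middle-dose expanded and high-dose sentinel cohorts open, the figure falls to 11.4 for the low dose and 5.6 + 5.6 = 11.2 for the high dose. If the middle-dose expanded cohort also runs into the last step, the middle dose falls to 5.6. The separation thus ranges from about 6 to 28 of 51.

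**The case for a change.** The best case for concern is that the bias formula is correct, the plan cannot rule drift out, and a display costs almost nothing. SAP 7.1 sends analysis results to sponsor staff for decisions about the program, so descriptive output can still have consequences. A site enrolls one cohort at a time, so even controls from the same weeks may come from other sites. A check made after a signal appears is weaker than one written down beforehand. Keeping the pooled interval as the main result and adding columns of 17 would seem harmless.

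Some of this stands. The 34 of 51 is right, the bias is real if rates drift, and the middle dose is exposed too if drift is not monotone. The site argument stands only as a possibility, because enrolling one cohort at a time does not stop a site from contributing to all three in turn. The claim that the columns would be harmless does not stand. They would rarely show real drift and would often suggest drift that is not there, and the same-cohort interval is so wide that failing to exclude zero says nothing. Nor can the absence of such a display be established: SAP 2 says table shells are prepared separately, SAP 6.7.1 refers to sponsor reporting standards, and parts of both documents are redacted. Subject-level AE listings are planned in any case, and the internal committee reviews 14-day safety data for each sentinel cohort as it enrolls.

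**Conclusion.** The concern does not hold. Comparing each dose group with all 51 placebo subjects is an open, prespecified choice, and with 17 per cohort it is the only comparison with useful precision. No hypothesis test or decision rule depends on these intervals. The harm is conditional on drift that no document indicates: none at flat rates, under 2 points of coverage for a doubling from 5% to 10%, and material only for changes such as 5/10/15% or 5/15/5% in one preferred term. The alternative cuts power from 37% to 0.3% for a 5% to 15% excess, and a by-cohort placebo table would detect the assumed drifts in 2.1% to 8.5% of cases. Whether to show it is a matter of taste in display, not a fault in the plan.

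This rests on planned, approximate group sizes, on randomization within dose cohort as implied by Tables 1 and 2, and on assumed background rates. Coverage was computed over all outcomes, not only those that pass the four-subject filter. Unredacted evidence of a large change in event rates between cohorts would be a reason to look again.

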### 5.2.2. Analyses for Continuous Data

#### 5.2.2.1. Geometric Means (GMs)

The GBS6 serotype-specific IgG, CCI antibody levels at each blood sampling timepoint will be summarized by geometric means (GMCs or CCI) and the associated 2-sided 95% CIs by vaccine group. The GMCs CCI will be calculated as the mean of the logarithmically transformed assay results and back transformed to its original units. The 2-sided, 95% CIs will be constructed by back transformation of the CIs for the mean of the logarithmically transformed assay results using Student's t distribution.

CCI

CCI

#### 5.2.2.4. Reverse Cumulative Distribution Curves (RCDCs)

Empirical RCDCs will be presented graphically by plotting the proportion of subjects vs GBS6 antibody levels for each serotype separately by vaccine group and at 1 month after vaccination blood sampling timepoint. The RCDCs at other timepoints may be generated. The lower limit of quantitation (LLOQ) and/or defined threshold values will be marked on the horizontal axis.

CCI

CCI

### 5.3. Methods to Manage Missing Data

#### 5.3.1. Immunogenicity Data

The LLOQ in  $\mu\text{g/mL}$  for each serotype of GBS IgG are set as follows: Ia, 0.0219; Ib, 0.0105; II, 0.0085; III, 0.0134; IV, 0.0045; V, 0.0745.

CCI

The GBS6 IgG, CCI antibody levels above LLOQ are considered accurate and their quantitated values will be reported. Values below the LLOQ or denoted as below limit of quantitation (BLQ) will be set to  $0.5 \times \text{LLOQ}$  for all analysis.

Values that are insufficient sera (QNS), indeterminate results, or recorded as “Not Done” will be set to missing. No imputation will be done for these missing values.

### 5.3.2. Safety Data

Standard algorithms on handling missing AE dates and missing AE severity will be applied as described in the Safety Rulebook Summary.

#### 5.3.2.1. Reactogenicity Data

For derived variables based on reactogenicity data, if any day of the 14-day e-diary is available, the ‘any day 1-14’ data will be considered as non-missing.

The reactogenicity data are collected through e-diary, which does not allow subjects to skip the question. Therefore, for a specific day, as long as the e-diary data is transferred for that day, all of the reactogenicity data for the subject on that day is non-missing. No missing reactogenicity data will be imputed other than what is described in [Section 3.6.2](#).

## 6. ANALYSES AND SUMMARIES

### 6.1. Primary Endpoint(s)

#### 6.1.1. Proportion of Sentinel-Cohort Subjects With Clinical Laboratory Abnormalities Following IP Administration at the 1 Week Follow-Up Visit

##### 6.1.1.1. Primary Analysis

**Endpoint:** Abnormalities in safety laboratory parameters as measured by FDA Grade.

- Analysis timepoints: Visit 2 (1 week after vaccination).
- Analysis population: Safety population.
- Analysis methodology: Descriptive summary statistics.
- Supporting objective: Primary safety objective.

#### Reporting results:

- Raw data: n and proportion will be presented for each FDA grade (1 thru 4) and laboratory parameters (Hemoglobin, Hematocrit ...) by vaccine group for sentinel cohort subjects only.

**Figures:** None

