#### **4.2. Exclusion Criteria**

Subjects with any of the following characteristics/conditions will not be included in the study:

1. Investigator site staff members directly involved in the conduct of the study and their family members, site staff members otherwise supervised by the investigator, or subjects who are Pfizer employees, including their family members, directly involved in the conduct of the study.
2. Participation in other studies involving investigational drug(s) within 28 days prior to study entry (Visit 0 for subjects in sentinel cohorts, Visit 1 for subjects in expanded cohorts) and/or during study participation. Participation in purely observational studies is acceptable.
3. Other acute or chronic medical or psychiatric condition, including recent (within the past year) or active suicidal ideation or behavior, or laboratory abnormality that may increase the risk associated with study participation or investigational product administration or may interfere with the interpretation of study results and, in the judgment of the investigator, would make the subject inappropriate for entry into this study. Chronic medical conditions include human immunodeficiency virus (HIV), chronic hepatitis B virus (HBV) infection (HBV surface antigen positive), and/or hepatitis C virus infection.

4. Male subjects and female subjects of childbearing potential who are unwilling or unable to use a highly effective method of contraception as outlined in this protocol for at least 3 months after the last dose of investigational product.
5. **For sentinel-cohort subjects only**, laboratory test results at the screening visit outside of the normal reference range. Refer to [Section 6.1](#) for additional guidance if abnormal laboratory test results are reported.
6. History of severe adverse reaction associated with a vaccine and/or severe allergic reaction (eg, anaphylaxis) to any component of the investigational product or any diphtheria toxoid-containing or CCI.
7. History of microbiologically proven invasive disease caused by group B streptococcus (*S agalactiae*).
8. Immunocompromised subjects with known or suspected immunodeficiency.

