#### Sentinel Cohort Subjects

Laboratory data will be collected for sentinel cohort subjects only. Data is collected during the screening visit, Visit 0 (-14 to -2 days prior to vaccination) and will be considered baseline data. For subjects with a rescreening visit, the rescreening laboratory results will be considered as the baseline data.

Day 1 is considered the baseline visit for the following assessments: Immunogenicity, [CCI] and vital signs.

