### 6.7.3. Laboratory Data

Descriptive summaries for laboratory abnormalities at 1 week after vaccination visit will be provided by vaccine group. Also, a listing of laboratory data will be generated.

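### The 1-week laboratory table ignores the screening grade, so for tests graded on fixed cut-offs an unchanged, in-range value can count as a Grade 1 abnormality after vaccination

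*SAP*

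**What the plan says.** The first primary endpoint is the proportion of sentinel-cohort subjects with laboratory abnormalities after the dose, at the 1-week visit (Protocol 2.1.2, SAP 3.1). SAP 6.1.1.1 turns this into "Abnormalities in safety laboratory parameters as measured by FDA Grade", with Visit 2 as the only timepoint. Under its reporting results, "n and proportion will be presented for each FDA grade (1 thru 4) and laboratory parameters" by vaccine group, for sentinel subjects only. SAP 6.7.3 adds that "Descriptive summaries for laboratory abnormalities at 1 week after vaccination visit will be provided by vaccine group", plus a listing of laboratory data.

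A baseline does exist on paper. SAP 3.4 says of the laboratory data: "Data is collected during the screening visit, Visit 0 (-14 to -2 days prior to vaccination) and will be considered baseline data". For a rescreened subject, "the rescreening laboratory results will be considered as the baseline data". Neither SAP 6.1.1 nor SAP 6.7.3 refers to it.

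Entry to the sentinel cohorts uses a different yardstick. Protocol 4.2, exclusion 5, rules out "laboratory test results at the screening visit outside of the normal reference range". The grades come from SAP Table 8, which sets fixed limits for some tests and multiples of the upper limit of normal (ULN) for others.

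**The concern.** Screening out abnormal laboratory values should make a 1-week abnormality readable as something that arose after the dose. That works only if normal at entry also means ungraded on Table 8. For tests with fixed cut-offs, nothing visible in either document secures this. A subject whose hemoglobin is within the laboratory's range but inside a Grade 1 band is eligible, shows the same value a week later, and enters the primary table as an abnormality.

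The table would then mix pre-existing low-grade values with new ones, and its reader could not tell them apart. The plan reports this endpoint as a within-group proportion. SAP 5.2.1.2 plans differences from placebo for tier-2 adverse events only, so the figure most open to carry-over is the one that is presented.

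**Working it through.** **Design figures.** Protocol Table 1 gives 40 sentinel and 81 expanded subjects per dose level: 3 × (40 + 81) = 363. Protocol 3.3 gives 6 × 52 + 51 = 363. Both match the planned total. Sentinel subjects number 3 × 40 = 120.

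**Group sizes.** The sentinel split by arm is redacted, so I assume it follows the overall ratio. Each active group then has 40 × 52/121 = 17.2 and placebo has 40 × 17/121 = 5.6 per dose level. SAP 5.2 reports one placebo group across dose levels, so its sentinel column is about 3 × 5.6 = 17.

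**Which tests can carry over.** An eligible value lies inside the reference range.

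- ALT, AST, alkaline phosphatase and bilirubin: Grade 1 starts at 1.1 × ULN. A value at or below 1.0 × ULN cannot be graded, so no carry-over is possible.
- Fixed cut-offs: carry-over is possible when the laboratory's limit meets the condition below.

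| Test | Grade 1 band (SAP Table 8) | Carry-over possible if |
|---|---|---|
| Hb, male (g/dL) | 12.5–13.5 | lower limit ≤ 13.5 |
| Hb, female (g/dL) | 11.0–12.0 | lower limit ≤ 12.0 |
| WBC, low (10^9/L) | 2.5–3.5 | lower limit ≤ 3.5 |
| Neutrophils (10^9/L) | 1.5–2.0 | lower limit ≤ 2.0 |
| Platelets (10^9/L) | 125–140 | lower limit ≤ 140 |
| WBC, high (10^9/L) | 10.8–15.0 | upper limit ≥ 10.8 |
| Eosinophils (10^9/L) | 0.65–1.5 | upper limit ≥ 0.65 |
| BUN (mg/dL) | 23–26 | upper limit ≥ 23 |
| Creatinine (mg/dL) | 1.5–1.7 | upper limit ≥ 1.5 |

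**How often.** The documents give no reference ranges, so this part is illustration. If female hemoglobin is normal with mean 13.3 and SD 0.9 g/dL (assumed), the share of eligible women already in Grade 1 is 6.9%, 5.3%, 3.8% or 0% for a lower limit of 11.0, 11.5, 11.7 or 12.0. If neutrophils are log-normal with median 3.8 and log-SD 0.35 (assumed), the share is 2.9%, 1.7% or 0% for a lower limit of 1.5, 1.8 or 2.0.

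**Effect on the table.** Let q be the share of eligible sentinel subjects who are in at least one Grade 1 band at screening and still there at Visit 2. The expected number is 120q. The chance of at least one in a group of 17 is 1 − (1 − q)^17. The chance that one of two groups of 17 has such a subject and the other has none is 2 × (1 − q)^17 × [1 − (1 − q)^17].

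| q (assumed) | Expected of 120 | At least one in 17 | One group has some, the other none |
|---|---|---|---|
| 0 | 0 | 0 | 0 |
| 2% | 2.4 | 29% | 2 × 0.709 × 0.291 = 41% |
| 5% | 6 | 58% | 2 × 0.418 × 0.582 = 49% |
| 10% | 12 | 83% | 2 × 0.167 × 0.833 = 28% |

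One unchanged value in a row of the table shows as 1/17 = 5.9% (Clopper-Pearson 95% CI 0.1% to 28.7%). Two show as 2/17 = 11.8% (1.5% to 36.4%). A count of new or worsened grades would show 0 in both cases.

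**The case against.** Five points can fairly be made for the plan.

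1. **The entry rule may be stricter than exclusion 5 alone suggests.** Protocol 6.1 and footnote a of the Schedule of Activities also refer to Section 7.5.3 for what counts as abnormal at screening. That section introduces the grading scale and is partly redacted. If graded values also exclude, no eligible subject starts at Grade 1 and the problem disappears. This stands as a limit: exclusion 5 itself names only the reference range, but the stricter reading cannot be ruled out.
2. **Placebo carries the same background.** This stands. The contrast is unbiased in expectation, provided the background is alike across the three dose cohorts that share the pooled placebo group. It does not correct the within-group proportion, and with about 17 against 17 chance imbalance remains.
3. **Only part of the endpoint is exposed.** This stands. The ULN-based tests are not affected. Grades are tabulated separately, so Grades 2 to 4 are largely untouched.
4. **A listing is planned and the analyses are descriptive.** In part. A reader could regrade 120 subjects' screening values by hand, but a listing is not a summary by baseline grade.
5. **The protocol endpoint does not say new or worsened.** This stands. The all-grades table is a literal implementation, and replacing it would change the analysis of a primary endpoint.

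A reader might infer that sentinel subjects will in fact enter already graded, or that the comparison with placebo is biased. The documents support neither: they give no reference ranges, and randomization balances the background in expectation.

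**Conclusion.** The point holds as a limited gap in the laboratory analysis. For hemoglobin, WBC, neutrophils, platelets, eosinophils, BUN and creatinine, the plan as visible does not stop an unchanged, in-range screening value from being reported as a Grade 1 abnormality after vaccination, and it leaves unused the baseline that would separate the two.

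The size cannot be fixed from the documents. It is zero if every reference limit lies outside the Grade 1 bands, or if graded values also exclude at screening. Otherwise each carried-over subject adds about 6 percentage points to a row of the table for a group of 17. That group size rests on the assumed sentinel split, and the values of q are illustrative.

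The consequence is an inflated within-group proportion, mainly at Grade 1, plus chance imbalance between small groups. It would go too far to call the whole laboratory endpoint invalid.

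**What to change.** - Keep the planned all-grades Visit 2 table in SAP 6.1.1.
- Add to SAP 6.1.1 and 6.7.3 a shift table of screening grade by Visit 2 grade for each graded test, by vaccine group. Grade the baseline value with the same Table 8 limits.
- With it, give the number and proportion of subjects whose Visit 2 grade is higher than their baseline grade. Read abnormalities that follow the dose from this count. It still includes ordinary week-to-week variation, so read it beside placebo.
- Define baseline for each parameter separately: the rescreening result where that test was repeated, otherwise the Visit 0 result. Protocol 6.2 repeats only the parameters that were abnormal.
- Reconcile exclusion 5 with Protocol 6.1, footnote a of the Schedule of Activities and Section 7.5.3, so that one meaning of abnormal at screening is stated.

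The cost is SAP wording and one more table, from data already collected. If no reference limit meets a Grade 1 band, the shift table will show that no subject started graded, and nothing is lost. Formally replacing the primary proportion with the new-or-worsened count is a separate decision. Protocol Section 9 and SAP Section 2 say that major changes to a primary endpoint or its analysis are also reflected in a protocol amendment, so it may need one. The fix above does not depend on it.
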